5 STUDY ENROLLMENT AND WITHDRAWAL

5.1 Selection of the Study Population

Participants in the experimental RV challenge studies at the UVA are largely drawn from the University community. These studies are widely known among the students and recruitment is primarily via an established database of individuals who have asked to be notified when a study will occur. Other recruitment activities include mass emails to the student population and “sidewalk chalk” advertising.

Recruitment of eligible volunteers will not be a limitation of this study. Our study site at the UVA has recently completed a separate study in which almost 800 volunteers were screened for participation in a challenge study over a 1-year period. The target of approximately 750 subjects screened over 3 years is well within the capacity of our site.

In this study, subjects will first be screened for neutralizing antibody to the two study viruses under an existing Institutional Review Board (UVA IRB #9948) approved screening protocol. Volunteers who are eligible to participate by serology (~15%) will then be contacted by email or telephone and offered the opportunity to participate in the challenge studies.

Given the complexity of the study schedule, we will plan to enroll approximately one-third of the study subjects each year for 3 years. The initial challenge will be done during the fall of each year and the second challenge will be done in the winter/spring. This schedule acknowledges the realities of the school calendar and will maximize retention of enrolled subjects. Subjects receive monetary compensation for participation and subject retention is excellent (in a recent study of 150 subjects, no subjects withdrew or were lost to follow-up). The planned enrollment over 3 years will allow variation of the cohort size in years 2 and 3 to ensure that the required sample size is available for analysis.

There are no gender or minority restrictions in this study. An age restriction is included in the study to provide greater homogeneity in the study population. In previous studies of this type at the UVA, approximately 70% of the subjects who participated have been white (72% of the University student body from which volunteer subjects are primarily drawn are white, not Hispanic) and approximately 59% of the participants have been female. The average age of the volunteers in these studies is generally in the early twenties. No gender or racial effects are expected for the analyses in this study. Pregnant women are excluded from the study because of the intentional challenge with RV that is a part of the study. Children are excluded from the study because the intentional challenge with RV cannot be ethically done in children.

5.2 Subject Inclusion Criteria

Subjects must meet all of the inclusion criteria in order to be eligible to participate in the study:

1. Are males and non-pregnant females, 18-40 years of age, inclusive.
2. Provide written informed consent prior to initiation of any study procedures.

3. Are able to understand and comply with planned study procedures and be available for all study visits.
4. Subject must have a serum neutralizing antibody titer of $\leq 1:2$ to RV type 39 and RV type 16.
5. Female subjects* must be using an effective birth control method[#] for at least 30 days prior to study enrollment and through 30 days post-rechallenge.

*for females who are not surgically sterile or post-menopausal

[#]Includes, but is not limited to, non-male sexual relationships, abstinence from sexual intercourse with a male partner, monogamous relationship with a vasectomized partner, male condoms with the use of applied spermicide, intrauterine devices, NuvaRing®, and licensed hormonal methods such as implants, injectables or oral contraceptives (“the pill”). Method of contraception will be captured on the appropriate data collection form.

6. Total IgE <200 IU/mL.
7. Hemoglobin ≥ 11 gm/dL for females and ≥ 13 gm/dL for males

5.2.1 Inclusion at Re-challenge

Subject must have participated in the first challenge and meet the following inclusion criteria to be eligible to participate in the re-challenge:

1. Are males and non-pregnant females, 18-41 years of age, inclusive.
2. Are able to understand and comply with planned study procedures and be available for all study visits.
3. Female subjects* must be using an effective birth control method[#] for at least 30 days prior to study enrollment and for the remainder of the study.

*for females who are not surgically sterile or post-menopausal

[#]Includes, but is not limited to, non-male sexual relationships, abstinence from sexual intercourse with a male partner, monogamous relationship with a vasectomized partner, male condoms with the use of applied spermicide, intrauterine devices, NuvaRing®, and licensed hormonal methods such as implants, injectables or oral contraceptives (“the pill”). Method of contraception will be captured on the appropriate data collection form.

5.3 Subject Exclusion Criteria

5.3.1 Exclusion at enrollment

Subjects meeting any of the exclusion criteria at baseline will be excluded from study participation:

1. Any abnormalities of the upper respiratory tract that might interfere with the procedures and assessments in the study
2. Any chronic upper respiratory illness
3. Any chronic lower respiratory disease or any acute lower respiratory illness in the 1 month prior to the challenge
4. Any bleeding tendency by history.
5. History of hypertension or currently on anti-hypertensive medication.
6. History of angina or other cardiac disease.

7. Any medical condition that in the opinion of the Investigator is cause for exclusion from the study.
8. Use of statins
9. Regular use of tobacco in the last 6 months (i.e., more than 2 days out of 7) or inability to refrain from smoking during the study.
10. Participation in any other clinical drug trial in the month prior to the study.
11. Household contacts/room mates who are under protective precautions due to immunosuppression

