2.3 Potential Risks and Benefits

2.3.1 Potential Risks

The participants in this study should expect to have a common cold and may experience nasal congestion, runny nose, sneezing, cough, sore throat, malaise, headache and chills but no significant risks to the health of the volunteers are anticipated from participation in this study.

Experience with the study model suggests that adverse outcomes requiring intervention (otitis media, bronchospasm or sinusitis) are rare. The virus pools used for the challenge in this study have been thoroughly safety tested and have been approved for investigational use by the Food and Drug Administration (FDA; IND 12934 for RV39 and IND 15162 for RV16). AEs will be reported to the UVA Human Investigations Committee for review.

RV infection has not been associated with any adverse effects on the fetus or newborn infant, however, women who are pregnant or nursing should not participate in the study. A pregnancy test will be done on all women who decide to participate in the study. All women who participate in the study must have a negative pregnancy test and be using an acceptable method of birth control as determined by the investigator.

RV infections are associated with asthma attacks in people who have asthma. Individuals who have asthma (as evidenced by a history of asthma, a history of wheezing, recurrent severe bronchitis or coughing associated with colds) will be excluded from the study.

The viruses which will be used for the study are RVs which were isolated from volunteers in previous studies. The donor volunteers were tested for human immunodeficiency virus (HIV; acquired immunodeficiency syndrome [AIDS]), hepatitis C and hepatitis B infection, and found to be negative. After isolation, the virus was cultured two times in the laboratory and has been tested for the presence of other pathogens which may cause infections in humans. The production and safety testing of the pools has been reviewed by the FDA and the pools have been granted INDs for experimental RV studies in human volunteers.

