5.3.2 Exclusion at Challenge

1. Any upper respiratory infection or allergic rhinitis in the 2 weeks prior to challenge.
2. Use of any common cold therapies in the 2 weeks prior to challenge (see list below*)
* for example: non-steroidal anti-inflammatory medications, benedryl and other antihistamines, Sudafed, pseudoephedrine, phenylephrine, oxymetazoline, inhaled/intranasal steroids, leukotrienes, or any bronchodilators, (such as short acting b-2-agonists, long-acting b2-agonists, anticholinergics).
3. Female subjects* with a positive urine pregnancy screen on day of challenge

5.3.3 *for females who are not surgically sterile or post-menopausal Exclusion at Re-challenge

To be considered eligible to participate in the Re-challenge, subjects must meet the eligibility criteria as listed above in both Inclusion and Exclusion Criteria. In addition, they must not have any of the following Exclusion criteria:

1. Subject experienced an infection-related adverse event (e.g. bronchospasm, otitis media, sinusitis, fever ($T > 100.5^{\circ} F$)) following prior challenge.
2. Female subjects with a positive urine pregnancy screen on day of rechallenge

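### Section 5 omits the nursing exclusion and the history-based asthma definition that Section 2.3.1 relies on, so some volunteers the risk section keeps out meet no explicit exclusion

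*Combined protocol and SAP*

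**What the plan says.** Section 2.3.1 (Potential Risks) notes that rhinovirus infection is associated with attacks in people who have asthma, and describes who is to be kept out: "Individuals who have asthma (as evidenced by a history of asthma, a history of wheezing, recurrent severe bronchitis or coughing associated with colds". On reproduction it says that "women who are pregnant or nursing should not participate in the study".

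Section 14.4 (Informed Consent Process) states that the site principal investigator chooses subjects by the criteria in Section 5. The relevant items there are:

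- Section 5.3.1, item 3: "Any chronic lower respiratory disease or any acute lower respiratory illness in the 1 month prior to the challenge".
- Section 5.3.1, item 7: "Any medical condition that in the opinion of the Investigator is cause for exclusion from the study".
- Section 5.3.2, item 2: use of listed cold therapies in the two weeks before challenge. The list includes inhaled or intranasal steroids, leukotriene drugs and bronchodilators.
- Section 5.2, item 1: "Are males and non-pregnant females, 18-40 years of age, inclusive".
- Section 5.3.2, item 3: "Female subjects* with a positive urine pregnancy screen on day of challenge".

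Section 8.1.1 says that a health care professional takes the medical history by questionnaire in an interview, that the principal investigator reviews it for eligibility before enrollment, and that medical records are not consulted.

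**The concern.** The risk section and the eligibility list should describe the same population. Here the risk section is broader. A screener who works from Section 5 alone, as Section 14.4 directs, could pass a volunteer whom Section 2.3.1 describes as excluded.

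The stake is mainly participant safety. Asthma is the one condition that Section 2.3.1 singles out as liable to attacks from the virus being given. There is a smaller operational stake. Under Section 5.3.3, bronchospasm after the first challenge bars a subject from re-challenge, where the plan wants 35 per virus. Under Section 9.2.4, a serious adverse event judged related to the challenge infection stops further challenges until the DSMB has reviewed it.

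**Working it through.** No figure is at issue, so the check is a comparison of text. Each group named in Section 2.3.1 was looked for in Sections 5.2, 5.2.1 and 5.3.1 to 5.3.3, then in the visit procedures (Section 7), Section 8.1.1 and Appendix A.

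| Group in Section 2.3.1 | Stated consequence | Explicit item in Section 5 | Other cover |
|---|---|---|---|
| Pregnant women | Should not participate | Yes: 5.2 item 1, 5.2.1 item 1, 5.3.2 item 3, 5.3.3 item 2 | Urine screen before each challenge |
| Nursing women | Should not participate | None | None evident |
| Current asthma | Excluded | Yes: 5.3.1 item 3, as a chronic lower airway disease | Medication rule, item 7 |
| Past asthma or past wheeze only | Excluded, as evidence of asthma | None that names it | Item 7, or a broad reading of item 3 |
| Recurrent severe bronchitis, or cough with colds, none in the last month | Excluded, as evidence of asthma | None that names it | Item 7, or a broad reading of item 3 |

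**Nursing.** Every reproductive criterion in Section 5 concerns pregnancy or contraception. A urine pregnancy test does not detect lactation, and a nursing woman can meet the contraception requirement. Sections 5.1 and 14.5.1 likewise exclude pregnant women only. Nursing is not clearly a medical condition, so item 7 does not obviously reach it. It is also absent from the visit procedures and Appendix A.

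**Asthma.** Item 3 has two limbs: chronic disease, and an acute illness within one month. Active asthma falls under the first. The neighbouring items mark history explicitly where history is meant: item 4 (bleeding tendency), item 5 (hypertension) and item 6 (angina or other cardiac disease). Item 3 does not, so on its face it concerns present disease or a recent episode. Take a volunteer who had asthma in childhood, or who has wheezed only with past colds, has been well for more than a month and has used no listed drug for two weeks. That person meets no explicit exclusion. Section 2.3.1 treats the same history as evidence of asthma and says of that group: "coughing associated with colds) will be excluded from the study".

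**Remaining safeguards.** The medication rule catches only recent treatment. The total IgE limit in Section 5.2 is not a criterion on asthma history. Item 7 is discretionary, whereas Section 2.3.1 is worded as mandatory for asthma. The interview in Section 8.1.1 could bring the history to light, but the only specific content that section names is prohibited medication in the preceding two weeks. Because records are not reviewed, the interview is the only stated source of such history.

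**The case against.** The best reply is that Sections 2.3.1 and 5 belong to one protocol and should be read together. The parenthesis in Section 2.3.1 does not create free-standing exclusions for wheeze or bronchitis. It says how asthma is to be recognised, and item 3 already excludes asthma. A health care professional takes the history, the principal investigator reviews it, and item 7 is there for doubtful cases.

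Much of this stands. A reader might infer that Section 5 leaves asthma out altogether. That is wrong, because item 3 excludes current asthma and the medication rule and item 7 add cover. A reader might also infer that the questionnaire fails to ask about asthma or wheeze. The questionnaire is not in the documents, so that cannot be said.

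The combined reading still does not close the gap. Section 5 contains no pointer to the definition in Section 2.3.1, and Section 14.4 points selection to Section 5 alone. Two careful screeners could decide differently on the same volunteer, and both could cite the protocol. Nor does the combined reading help with nursing, which has no counterpart in Section 5 at all.

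Three further points limit the stakes. Section 2.3.1 says that nursing women should not participate, which is softer than its wording on asthma, and it reports no known adverse effect of rhinovirus on the fetus or newborn. It also calls outcomes such as bronchospasm rare. Section 4.2 allows the final cohort to be resized for attrition, so the loss of a few re-challenge subjects is partly provided for.

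**Conclusion.** The inconsistency is real and should be corrected. The nursing half holds in full. The asthma half holds in a narrower form: Section 5 covers current asthma, but it neither carries over nor cross-references the history-based definition. The groups affected are nursing women with a negative pregnancy test, and volunteers with only past, untreated asthma, wheeze or the related histories. No endpoint, power calculation or planned analysis is affected.

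The number of people concerned cannot be given. A reader might apply a general-population prevalence of asthma history to the 80 subjects to be challenged. The documents give no such prevalence. Section 11.3.2 also describes those 80 as already reviewed against the other eligibility criteria, and some people with such a history would have been removed by item 3 or item 7. The result would not estimate how many pass through the gap.

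The conclusion assumes that Section 5 governs selection, as Section 14.4 says, and that no eligibility rule sits in the questionnaire, the Manual of Procedures or the few protocol pages that were not available to check.

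**What to change.** Reconcile Section 2.3.1 with Sections 5.2 and 5.3 so that both describe the same population. For nursing, and for each element of the history-based asthma definition, either the item appears in the Section 5 lists or Section 2.3.1 stops describing it as a ground for keeping someone out. Which version is right is for the sponsor and investigator to decide. Section 5.3.3 applies the listed criteria again at re-challenge, so the reconciled wording should be checked there too. The questionnaire in Section 8.1.1 should then capture every item retained.

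The cost is amendment wording, a check of the questionnaire, and possibly a few more screen failures. Those failures should not be assumed to be free. Section 11.3.2 goes from about 96 volunteers with a matched tetramer to 80 challenged, but that difference of 16 is already the allowance for the other eligibility criteria, not spare capacity.

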5.3.2 Exclusion at Challenge

1. Any upper respiratory infection or allergic rhinitis in the 2 weeks prior to challenge.
2. Use of any common cold therapies in the 2 weeks prior to challenge (see list below*)
* for example: non-steroidal anti-inflammatory medications, benedryl and other antihistamines, Sudafed, pseudoephedrine, phenylephrine, oxymetazoline, inhaled/intranasal steroids, leukotrienes, or any bronchodilators, (such as short acting b-2-agonists, long-acting b2-agonists, anticholinergics).
3. Female subjects* with a positive urine pregnancy screen on day of challenge

5.3.3 *for females who are not surgically sterile or post-menopausal Exclusion at Re-challenge

To be considered eligible to participate in the Re-challenge, subjects must meet the eligibility criteria as listed above in both Inclusion and Exclusion Criteria. In addition, they must not have any of the following Exclusion criteria:

1. Subject experienced an infection-related adverse event (e.g. bronchospasm, otitis media, sinusitis, fever ($T > 100.5^{\circ} F$)) following prior challenge.
2. Female subjects with a positive urine pregnancy screen on day of rechallenge

5.4 Treatment Assignment Procedures

5.4.1 Randomization Procedures

All volunteers will be challenged with RV16 at the first challenge. Randomization of subjects for challenge with either RV16 or RV39 at the second challenge will be done using GraphPad® software with randomization blocks of ten. The challenge pool used will be recorded on source documents and transferred to the data collection form (DCF).

5.4.2 Masking Procedures

This study does not involve any blinding or masking procedures. Volunteers will not be told which virus they are receiving for the second challenge. The identity of the virus inoculated for the second challenge is of no clinical significance and this information will not be shared with the subjects.

5.4.3 Reasons for Withdrawal

Withdrawal Criteria

Subjects may be withdrawn from the study (i.e., from any further study procedure but not from analyses) for the following reasons:

- At their own request or at the request of their legally authorized representative.
- If the volunteer fails to comply with study procedures.
- If they are lost to follow-up.

In all cases, the reason for and date of withdrawal must be recorded in the DCF. The subject must be followed up to establish whether the reason was an AE, and, if so, this must be reported.

The investigator or appointed representative must make every effort to contact subject lost to follow-up. Attempts (3 attempts) to contact such subject, and the method of contact, must be documented in the subject's records (e.g., dates and times of attempted contact).

Any subject may be withdrawn from the study at the discretion of the investigator. The subject is also free to terminate participation at any time.

Subjects who meet exclusion criteria for the re-challenge will not be followed beyond the week 15 study visit unless they have an adverse event that must be followed by protocol.

5.4.4 Handling of Withdrawals

Withdrawn Subject Data Collection

The principal investigator (PI) and/or other investigator involved in the study will document the reason for the subject withdrawal on the termination page of the DCF as follows:

- Lost to follow-up: subjects who leave the study without notification, or do not attend the study visit or cannot be contacted by phone. Intensive efforts should be made to locate and recall them if possible and to determine their health status at a minimum.
- AE: an AE event form must be completed.
- Adverse laboratory event: this reason should be stated when a laboratory value is interpreted as a clinically significant abnormal value not explained by a laboratory error, or being not a known or abnormal value commonly observed in this type of population.
- Deviation from protocol.
- Consent withdrawn.
- Other: if the above mentioned reasons are not applicable, then the reason will be specified.

Subjects who withdraw from the study during the symptomatic portion of the virus challenge will be re-contacted approximately 14 days after the challenge to document resolution of the viral illness. Subjects who withdraw at other times in the study will not require any study follow-up. Attempts to contact subjects who are lost to follow-up will be as described in section 5.4.3.

5.4.5 Termination of Study

Although the study Sponsor has every intention of completing the study, it reserves the right to terminate the study at any time for clinical or administrative reasons. Reasons for termination include, but are not limited to, study closure due to Data and Safety Monitoring Board (DSMB) review and recommendation, and at the discretion of DMID.

6 INVESTIGATIONAL PRODUCT

6.1 Investigational Product Description

6.1.1 Acquisition

The challenge viruses used for this study are in the possession of the sponsor-investigator ([name]).

6.1.2 Formulation, Packaging, and Labeling

The virus pools consist of clarified cell culture supernatants of Eagle's minimal essential media supplemented with 10% fetal bovine serum. The pools are packaged in cryovials labeled to identify the pool and lot number, and are stored at -60 °C.

6.1.3 Product Storage and Stability

Vials of the RV pool are stored at -60 °C until thawed for use for the challenge. The vials are diluted in lactated ringer's solution for human use to produce the desired dilution for the human challenge. The diluted virus is prepared on the day of challenge and is kept cool on wet ice until the inoculation of volunteers is completed. The stability of the virus is documented by back titration of the diluted inoculum pool to demonstrate that the expected virus titer was delivered.

The virus pools are stored at -60 °C or below. The challenge pools are stable under these conditions for an indefinite period of time measured in decades.

